3.1 Sample size

In this single-centre study we wish to analyse 40 consecutive patients in whom a complete set of data can be obtained. From our previous experiences the incidence of AF in our intensive care unit is approximately 13.8%. Therefore in a sample size of 40 patients we would expect 2-3 patients to develop AF. This would allow us the opportunity to investigate any correlation between the changes in HRV preceding the onset of AF and investigate our secondary objectives to inform a larger clinical trial.

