Whilst both monitoring devices are capable of recording continuous ECG and HRV data, it remains unclear how robust the data are with regards to interference and artefacts. In particular, it is unclear how each monitoring device will operate whilst patients are undergoing daily care maneuvers such as physiotherapy, washing and patient repositioning. Furthermore, it has not been described yet how HRV is affected by interventions such as mechanical ventilation, administration of inotropes or vasopressors, paralysis agents, or renal replacement therapy. The current study aims to elucidate the impact of these standard interventions on HRV and the robustness of HRV measurement between the Isansys wireless monitor and the gold-standard HRV monitoring technique. This feasibility study will aide decision making with regard to which device will be most suitable for further studies of HRV in critically unwell patients.

2. Trial Objectives, Design and Statistics

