2.1 Trial objectives

The **primary objective** is:

- To describe the robustness of data on HRV data obtained by two different monitoring systems in daily care of critically ill patients. The Isansys wireless monitoring device will be compared to the gold-standard holter monitoring device for ECG analysis.

The **secondary objectives** are:

- To identify the most suitable and cost-efficient device for HRV monitoring in critically ill patients.
- To define amendments in data capture and analysis required to proceed to a larger clinical trial
- To generate preliminary data on the variation of HRV in a critical care patients.

Primary outcome:

- Number of interpretable monitoring epochs in each HRV monitoring system after elimination of artefacts, extra beats and interference

Secondary outcomes:

- Correlation and comparison of HRV time, frequency and non-linear measures between the Isansys monitoring device and the gold-standard holter monitoring system.
- Correlation between HRV and onset of arrhythmias (ventricular or atrial)
- Correlation between HRV and cardiorespiratory events that commonly occur in critically ill patients, including, oxygen desaturation (SaO₂<85%), variations in blood pressure of >20%, change in ventilatory support, muscle paralysis, position of the patient, administration of vasopressors (e.g. noradrenaline and vasopressin).
- Nurses' and medical staff's perception of the usability of both monitoring systems in daily routine

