3.2 Inclusion criteria

- Adult patients ≥ 18 years
- Expected ICU stay > 48 hours
- Sinus rhythm on admission
- Mechanically ventilated patients

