4.3 Schedule of study procedure

With informed consent, the following routinely recorded clinical and laboratory data will be collected:

- Baseline demographics and comorbidities
- Administration of beta blockers or anti-arrhythmics
- Administration of sedative agents (general anaesthetics/opioids/benzodiazepines)
- Reasons for admission to ICU
- Daily biochemistry and haematology results
- Severity of illness scores, including APACHE II and daily SOFA scores
- Daily CAM ICU scores / delirium
- Daily cardiac rhythm as per nursing entry or clinical diagnosis
- Daily clinical parameters, including medications (vasopressors/ionotropes/steroids/muscle relaxants) and organ support
- Daily AKI stage, including treatment with RRT

After obtaining informed consent, continuous ECG data will be recorded using the two different devices. ECG data will then be processed to derive HRV using the methodology described by the European Society of Cardiology Taskforce guidelines.² Processing of ECG data entails checking

for and removal of extrasystole and ectopic beats with interpolation of QRS complexes as described elsewhere.² Continuous 24 hour ECG recording will then be divided into 5 minute epochs for which short term HRV values will be calculated. HRV will be calculated in the time domain, frequency domain and non-linear domains for each 5 minute epoch. Entire 24 hour ECG recordings will be used for long term HRV measures in the time domain, frequency domain and non-linear domains as described the Taskforce guidelines.² HRV data will then be analysed according to that described in the statistical methodology and analysis section. HRV data will be calculated by the Medical Engineering and Clinical Physics department at the Royal Liverpool and Broadgreen University Hospital. They will be blinded to any patient identifiable or clinical information.

Daily data will be collected until day 5 in ICU, day of discharge from ICU or day of death (depending on what occurs first). In addition, we will record ICU and hospital length of stay, ICU and hospital mortality and occurrence of arrhythmias during ICU stay, after 30 days, and after 90 days following enrollment. Data will be collected by accessing routinely available results in the patients' medical records, and if necessary, by contacting the patient's General Practitioner (GP).

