4.5 End of Study Definition

The study will end after a total of 30 evaluable patients with complete data collection have been enrolled.

5. Laboratories

Not applicable

6. Assessment of Safety

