6.2 Safety of Heart rate variability monitoring devices

Device 1

Isansys Lifetouch Sensor is a fully CE marked medical device. The monitoring system includes single use wearable adhesive patches which are supplied in at least three sizes, depending on the age and size of the patient. Each Lifetouch provides the following clinical data continuously for a period of up to 5 days:

- Heart rate
- Respiration rate
- Real time heart rate variability
- Visualization of the ECG
- 3 axes accelerometer output

The Isansys Lifetouch Sensor is fully wireless and battery operated. The battery is not accessible to the patient or staff. All Isansys Lifetouch Sensor are single patient use and will be disposed off by following local procedures Information is transmitted wirelessly to a mobile patient status engine (ipad) via wifi and Low energy Bluetooth connectivity. The patient status engine Gateway is supplied in a protective medical grade bezel frame sealed in such a way to allow it to be cleaned with standard disinfecting/sterilising liquids or wipes. The device is safe with all other intensive care monitoring.

Device 2

Ambulatory Holter ECG monitoring is a standard of care used by the cardiorespiratory department. Ambulatory holter monitoring involves attaching a 12 lead ECG to the patient in the standard ECG lead configuration using standard ECG adhesive dots. Holter monitors record continuously for 72 hours onto a memory card and are entirely battery operated with no new electrical connection to the patient. Following 72 hours the memory card is analysed using software provided by the holter monitoring company. The software is of medical standard and provides HRV data, data on the number of interpretable episodes, data on ectopic beats and arrhythmias. Ambulatory holter monitoring is already in routine clinical use within the Royal Liverpool and Broadgreen University Hospital. They are CE marked and validate for use on patients.

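### The analysed group and the end of study both depend on complete data, although usable data is the primary outcome, so failed recordings can drop out of the result

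*Protocol*

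**What the plan says.** The primary objective (protocol, section 2.1) is "To describe the robustness of data on HRV data obtained by two different monitoring systems in daily care of critically ill patients". The primary outcome in the same section is "Number of interpretable monitoring epochs in each HRV monitoring system after elimination of artefacts, extra beats and interference". The introduction explains why the question is open: "it remains unclear how robust the data are with regards to interference and artefacts", in particular during physiotherapy, washing and repositioning.

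Two rules decide who counts. Section 3.1 states: "we wish to analyse 40 consecutive patients in whom a complete set of data can be obtained". Section 4.5 states: "The study will end after a total of 30 evaluable patients with complete data collection have been enrolled". Neither section defines a complete data set or an evaluable patient.

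Section 4.2 keeps patients enrolled through a consultee in the analysis if they die or never regain capacity. The protocol has no corresponding sentence for patients whose recording failed or was cut short, and does not ask for such failures to be counted by device.

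**The concern.** The study is meant to find out how much usable data each device produces in routine intensive care. A patch that comes off, a wireless link that drops or a Holter that stops early is part of the answer. If such a patient does not count as complete, sections 3.1 and 4.5 allow that patient to be left out while recruitment goes on until enough complete patients have accrued. The analysed group is then selected on something closely tied to the primary outcome.

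Two consequences follow. The yield of both devices is expected to look better than it was. And because completeness is required per patient, failure of one device can also remove the other device's good recording, so a difference in failure rate may not appear at all. That difference bears directly on two secondary objectives: choosing the more suitable device and deciding what to change before a larger trial.

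**Working it through.** **What the protocol gives.** It states no device failure rate, no expected yield and no number of patients expected to be incomplete, so there is no figure on this point to reproduce. The only calculation in section 3.1 concerns expected atrial fibrillation cases and says nothing about completeness.

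**Which losses the rule can hide.** Section 4.3 says: "Continuous 24 hour ECG recording will then be divided into 5 minute epochs for which short term HRV values will be calculated". That is 24 × 60 / 5 = 288 epochs per 24 hours.

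- Epochs spoiled by artefact inside a retained recording reduce that device's count and stay visible.
- Recordings that are missing altogether, or truncated, lose their epochs from the count only if the patient is excluded as incomplete. This is the loss at issue.

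**Illustration of direction (all inputs assumed).** Let f be the share of patients in whom a device's recording fails, g the interpretable share in a good recording and b the share in a failed one.

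- All enrolled patients: yield = (1 − f) × g + f × b.
- Only patients complete on both devices: yield = g.
- Share of patients kept, if failures are independent: (1 − f for Isansys) × (1 − f for Holter).

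Take g = 90% for both devices, b = 30% and a Holter failure share of 5%. Holter yield over all patients is 0.95 × 90 + 0.05 × 30 = 87%. For Isansys at f = 20% it is 0.80 × 90 + 0.20 × 30 = 78%. The share kept is 0.80 × 0.95 = 0.76, so 40 / 0.76 = 52.6, that is 53 patients, must be enrolled to reach 40 complete ones.

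| Isansys f | Isansys yield, all | Holter yield, all | True gap (points) | Gap, complete only | True gap if b = 0 | Enrol for 40 | Enrol for 30 |
|---|---|---|---|---|---|---|---|
| 10% | 84% | 87% | 3 | 0 | 4.5 | 47 | 36 |
| 20% | 78% | 87% | 9 | 0 | 13.5 | 53 | 40 |
| 30% | 72% | 87% | 15 | 0 | 22.5 | 61 | 46 |

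With b = 0 the all-patient yields are 85.5% for Holter and 81%, 72% and 63% for Isansys. Across both choices of b, the 90% shown under complete-only analysis is 3 to 27 points too high.

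The complete-only gap is exactly zero because g was set equal for the two devices. If the devices also differ in artefact within good recordings, that part of the gap would still be reported. Only the part due to failed recordings disappears.

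**Consistency with other sections.** Patients chosen for having complete data are not simply consecutive, the other word used in section 3.1. The retention of patients who die (section 4.2) also fits poorly with a completeness requirement, since death can cut a recording short.

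**The case against.** The strongest reply is that complete is undefined and may be lenient. In sections 4.3 and 4.4 collecting data refers to clinical records and follow-up to day 90, so section 4.5 could mean no more than a finished case record. If so, failed recordings stay in and there is no bias. If it means that both recordings exist, only recordings missing altogether are lost. Much of the loss that interests the investigators is artefact within recordings, which remains visible on any reading. All this stands, and it limits the size of the problem. It does not remove it: nothing in the protocol rules out the strict reading, and no sentence retains failed recordings.

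A second reply is that analysis sets belong in a statistical analysis plan. Detail does. But the protocol itself states the analysed group and the stopping count, and a later plan could not restore excluded patients without contradicting it.

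A reader might also infer stronger claims, which the documents do not support:

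- *That many eligible patients cannot be complete by design*, because eligibility requires "Expected ICU stay > 48 hours" while "Holter monitors record continuously for 72 hours onto a memory card". The 72 hours describe the Holter's recording length and are nowhere made a condition of being evaluable. The analysis units are 5-minute epochs and 24-hour recordings, two of which fit within 48 hours. No length-of-stay figure is given.
- *That the sickest and the quickest-recovering patients are excluded.* Section 4.2 keeps consultee-enrolled patients who die. Section 4.3 ends daily data at day 5, discharge or death, so on that schedule an early death or discharge can still be complete.
- *That incomplete patients are formally replaced.* There is no replacement rule. Continued enrolment follows only from the stopping count in section 4.5.

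**Conclusion.** The point holds. Sections 3.1 and 4.5 make the analysed group and the end of study conditional on complete data in a study whose primary outcome is data yield. Followed as written, they can remove failed or truncated recordings, and no other section keeps them in.

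The expected direction is upward for yield and towards no difference for the device comparison, provided that failed recordings yield less than retained ones and are treated as incomplete. The size cannot be derived from the documents. The 3 to 27 points of overstatement and the 3 to 22.5 points of hidden gap in the table rest wholly on assumed inputs and the strict reading of complete. If complete refers only to the clinical record, the effect is nil. Because the rule touches the primary outcome and is cheap to reword, it should be corrected before analysis.

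**What to change.** - In sections 3.1 and 4.5, define the primary analysis set as all consented patients in whom the devices were applied, and end the study on the number enrolled. Section 3.1 gives 40 and section 4.5 gives 30, so settle one target at the same time.
- For each device, take as denominator the 5-minute epochs scheduled while the patient is in ICU and within the planned recording time. State that time once, the same for both devices, since section 6.2 gives 72 hours for the Holter and up to 5 days for the patch.
- Count epochs lost to detachment, transmission loss or device failure as non-interpretable. Censor only at death, ICU discharge or withdrawal.
- Restrict complete pairs to the Bland-Altman analysis, and report the recordings lost, by device and reason.

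Cost: a change of wording, and a record of the start, stop and reason for loss of each recording, which is not in the data list of section 4.3. The reported yield may look less favourable, and the Bland-Altman analysis may have fewer complete pairs than planned.

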3.3 Exclusion criteria

Any of the following criteria:

- Non-ICU patient
- Known Atrial Fibrillation
- Dependent upon pacemaker
- Previous cardio-thoracic surgery
- Expected ICU stay < 48 hours

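### Section 3.1's expected 2-3 AF cases do not follow from its own inputs: 13.8% of 40 patients is 5.5, and no lower rate is stated

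*Protocol*

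**What the plan says.** Section 3.1 of the protocol sets the number of patients: "In this single-centre study we wish to analyse 40 consecutive patients in whom a complete set of data can be obtained". It then gives one rate: "From our previous experiences the incidence of AF in our intensive care unit is approximately 13.8" per cent. From these two inputs it concludes: "Therefore in a sample size of 40 patients we would expect 2-3 patients to develop AF". The use made of that count follows at once: "This would allow us the opportunity to investigate any correlation between the changes in HRV preceding the onset of AF", together with work on the secondary objectives.

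Three other places bear on the figure:

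- **Sample size.** Section 4.5 reads "The study will end after a total of 30 evaluable patients with complete data collection have been enrolled", and the synopsis also gives 30 as the number of subjects.
- **Eligibility.** Section 3.2 requires "Sinus rhythm on admission", and section 3.3 excludes patients with "Known Atrial Fibrillation".
- **Recording time.** The Introduction and section 6.2 describe Holter recording over 72 hours; section 6.2 gives up to 5 days for the wireless patch.

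Section 3.1 offers no other number in support of the sample size: no precision for the limits of agreement, no power and no effect size.

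**The concern.** The sentence with the count opens by presenting it as a consequence of the incidence just given. A reader who multiplies the two inputs gets roughly double the stated count. Either the multiplication is wrong, or a different rate was used and is not shown. On both readings section 3.1 cannot be reproduced as it stands.

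The stake is the usefulness of the sample-size paragraph. HRV in relation to arrhythmia onset is a secondary outcome, and AF is the only arrhythmia for which the protocol gives an expected number. Someone judging what can be learned about HRV before AF needs to know whether to expect two or three episodes or five or six, and at present the text supports both.

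**Working it through.** **Inputs**

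- AF incidence p = 0.138 (section 3.1, stated as approximate)
- N = 40 (section 3.1); N = 30 (synopsis and section 4.5)
- Stated expected count: 2-3 (section 3.1)

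**Step 1. Attempt to reproduce the plan's figure.** Expected cases = N × p.

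- N = 40: 40 × 0.138 = 5.52
- N = 30: 30 × 0.138 = 4.14

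Neither falls in 2-3. At N = 40 the product exceeds the stated range by a factor of 5.52 / 3 = 1.8 to 5.52 / 2 = 2.8.

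**Step 2. What would give 2-3?**

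- Rate needed at N = 40: 2 / 40 = 5.0% to 3 / 40 = 7.5%
- Rate needed at N = 30: 2 / 30 = 6.7% to 3 / 30 = 10.0%
- Patients needed at 13.8%: 2 / 0.138 = 14.5 to 3 / 0.138 = 21.7

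None of these rates or patient numbers is in the protocol. Rounding of an approximate 13.8% cannot reach 7.5%.

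**Step 3. Could loss of patients explain it?** If half of the 40 were lost, 20 × 0.138 = 2.76, which would fit. But no such loss is stated, and the 40 are defined as patients who already have complete data. A loss of 25% gives 30 × 0.138 = 4.14, which does not fit.

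**Step 4. Chance variation.** Treat the AF count as binomial (independent patients, common rate 0.138).

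| N | Mean | Median | 95% range | P(2 or 3 cases) | P(3 or fewer) |
|---|---|---|---|---|---|
| 40 | 5.5 | 5 | 2-10 | 0.16 | 0.18 |
| 30 | 4.1 | 4 | 1-8 | 0.32 | 0.39 |

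Observing 2 or 3 cases in 40 would therefore be unremarkable, but 2-3 is not the expected number, and section 3.1 presents it as such.

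**The case against.** The best defence is that the authors discounted the rate. The 13.8% describes the unit as a whole, and the text does not say whether it counts new-onset AF only or any AF. Enrolled patients start in sinus rhythm without known AF, and the Holter runs for 72 hours, so the rate that matters here may well be lower. A discount to 5.0-7.5% (36% to 54% of 13.8%) is conceivable. This stands as a reason not to declare 5.5 the true expectation. It does not rescue the sentence, because no discount is mentioned and the count is presented as following from 13.8% and 40.

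The second defence concerns importance, and most of it stands. This is an observational feasibility study. The primary outcome is the number of interpretable epochs, and AF onset is part of one secondary outcome. No power calculation or stopping rule depends on the count.

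A reader might infer more than the text supports:

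- *That the sample is too small.* The error runs the other way: at 13.8% more AF cases are expected than stated.
- *That 40 was derived from the AF count alone.* Section 3.1 names 40 first and then says what it would allow. The count is the only number offered in support, which is not the same as the source of the choice.
- *That the wrong count will be carried into the design of the larger trial.* The text says that investigating the secondary objectives will inform that trial; it does not say that this expected count will be used to size it.

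**Conclusion.** The inconsistency is real. On the protocol's own inputs the expected number of AF cases is 5.5 in 40 (95% range 2-10) or 4.1 in 30 (1-8), against a stated 2-3. The stated count would need a rate of 5.0-7.5% in 40 patients, and none is given. The ranges assume independent patients with a common rate of exactly 13.8%.

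The documents do not settle which number is wrong. If 13.8% is the rate for eligible patients during the recording, the count is wrong and understates events. If a lower rate was intended, the count may be right and the rate is missing. In neither case are the primary outcome or the device comparison affected.

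This ranks as a point that should be fixed, because it is the only quantitative support given for the sample size. It does not threaten the study.

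**What to change.** 1. Settle whether the sample size is 40 (section 3.1) or 30 (synopsis and section 4.5). That conflict is a separate matter, but the count cannot be restated until it is resolved.
2. Preferably, state in section 3.1 the new-onset AF rate expected in eligible patients (in sinus rhythm when admitted, no known AF) within the recording window, say where it comes from, and recompute the expected count and its range from it.
3. If 13.8% is already that rate, say so and correct the count to about 5-6 in 40 patients (95% range 2-10) or about 4 in 30 (1-8).

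Simply printing 5.5 without confirming that 13.8% applies to the enrolled population could replace an unexplained low figure with one that is too high.

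The cost is one or two sentences in section 3.1, plus a look at the unit's own data if a rate for eligible patients has to be found. Correcting the count requires no change to recruitment, recording or the primary analysis.

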3.2 Inclusion criteria

- Adult patients ≥ 18 years
- Expected ICU stay > 48 hours
- Sinus rhythm on admission
- Mechanically ventilated patients

3.3 Exclusion criteria

Any of the following criteria:

- Non-ICU patient
- Known Atrial Fibrillation
- Dependent upon pacemaker
- Previous cardio-thoracic surgery
- Expected ICU stay < 48 hours

3.4 Criteria for Premature Withdrawal

A patient may request to be withdrawn from the study at any time, for any reason, without prejudice and without an impact on their clinical care. A patient may also be withdrawn from the study at the request of his/her legal representative or clinical team, for any reason.

4. Study Procedures

